GDC-0853 is considered to have a low potential to cause QT interval prolongation or to directly affect other cardiovascular parameters at therapeutic exposures. A minimal increase in corrected QT (QTc; 7 msec or 3%) interval was noted at 45 mg/kg in the single-dose, cardiovascular, safety, pharmacology study in telemetry-instrumented dogs. Cardiac safety will be evaluated in all patients at baseline and throughout the study, with routine monitoring of vital signs, including heart rate and blood pressure, collection of ECGs, and reporting of cardiac adverse events.

Malignancy

The impact of BTK inhibition on the development of malignancies is not known; however, malignancies are considered a potential concern for all immunomodulatory agents. Patients with a history of cancer within 10 years before screening will be excluded *initially* from participation in Study GA29350 (and therefore from Study GA30067), except for basal or squamous cell carcinoma of the skin that has been excised and is considered cured and in situ carcinoma of the cervix treated with apparent success by curative therapy more than 1 year prior to screening. All malignancies are considered adverse events of special interest with expedited reporting requirements to the Sponsor.

Vasculitis

The risk to human safety based on toxicological findings of vascular inflammation in animal studies is uncertain. As a safety risk-mitigation measure, patients with a history of vasculitis, including RA associated vasculitis, will be excluded *initially* from Study GA29350 (and therefore from Study GA30067 and complete blood counts (CBCs), creatinine levels, and urinalysis findings will be monitored in all patients during both studies: Studies GA29350 and GA30067. Study drug should be discontinued in any patient who develops an adverse event of vasculitis, and the patient should enter the safety follow-up period.

Overall, GDC-0853 has been well tolerated in Phase I healthy subjects and in patients with hematological malignancies. On the basis of the compelling mechanism for BTK inhibition in RA, the risk-benefit ratio for this study is deemed acceptable. The long-term safety profile of GDC-0853 will be further characterized in this open-label Phase II study, and a robust safety monitoring plan that describes the potential risks for GDC-0853 and the risk-mitigation strategies to minimize risks for the patients in this trial is provided in Section 5.1.

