4.2.2.1 GDC-0853 Dose and Administration

The GDC-0853 dose regimen is oral 200 mg BID. Patients will receive GDC-0853 approximately every 12 hours for 52 weeks. Patients should be directed to take one dose (a total of 4 tablets) BID (total of 8 tablets each day). On clinic visit days during the first 12 weeks of the study, patients should be instructed that the a.m. dose of GDC-0853 will be administered in the clinic, except for Day 1, since the last dose of GDC-0853 for Study GA29350 is the a.m. dose on Day 84 for all patients. For patients continuing into the OLE Study GA30067, the first open-label dose of GDC-0853 should be the p.m. dose (may be taken at home) on Day 84 (which is Day 1 of Study GA30067). After Week 12, GDC-0853 administration in the clinic is not required.

A dose reduction of GDC-0853 for specific safety events is permitted (see Table 3). For a potential dose reduction for other adverse events not listed in the table, please consult the Medical Monitor. If dose reduction is indicated, the dose of GDC-0853 may be reduced from 200 mg BID to 200 mg QD. In this case, patients should be directed to take one dose (a total of 4 tablets) QD in the morning (total of 4 tablets each day).

Guidelines for dose reduction and treatment interruption or discontinuation are provided in Section 5.1.

GDC-0853 may be orally administered with or without food. The dates and times of the most recent prior meal, last dose of GDC-0853 (prior to clinic visit), and timing of GDC-0853 administration in clinic should be recorded at each clinic visit. In addition, any use of PPIs, H2-receptor antagonists (H2RAs), and/or other antacids (e.g., Maalox®, Pepto-Bismol®, Rolaids®) should be recorded as concomitant medications, including time and date of last administration. Administration of GDC-0853 should be staggered with antacid use (i.e., GDC-0853 should be taken 2 hours before or 2 hours after the antacid).

GDC-0853—Genentech, Inc. 51/Protocol GA30067, Version 2

At study visits, sufficient GDC-0853 tablets will be dispensed to complete dosing until the next scheduled visit. When GDC-0853 is administered at the site, it will be administered under supervision of study personnel, and the amount of GDC-0853 dispensed must be recorded.

4.2.2.2 *GDC-0853 Compliance*

The following measure will be taken to assess patient compliance with study drug: patients will be directed to bring any used and unused bottles to each visit.

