4.5.2 Study Treatment Discontinuation

Patients must discontinue study treatment if they experience any of the following:

- Pregnancy
- Anaphylaxis or other severe hypersensitivity reaction

- Malignancy (with the exception of non-serious local and resectable basal or squamous cell carcinoma of the skin)
- Any serious infection or infection requiring treatment with an IV antimicrobial agent
- Any prohibited medication as defined in Section 4.3
- Any Grade 3 or greater thrombocytopenia (National Cancer Institute Common Terminology Criteria for Adverse Events [NCI CTCAE v4.0])
- Any Grade 4 neutropenia (NCI CTCAE v4.0)
- Failure to achieve a 20% improvement in both SJC and TJC (relative to baseline values in Study GA29350) at Week 24

Patients who discontinue study treatment prematurely for the reasons listed above will be asked to return to the clinic for an early termination visit (see Section 4.5.1) followed by 8 weeks of safety follow-up.

The primary reason for study treatment discontinuation should be documented on the appropriate eCRF. Patients who discontinue study treatment prematurely will not be replaced.

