5.1.1.8 Vascular Inflammation

Vascular inflammation (vasculitis) was observed in dogs administered GDC-0853 at \geq 10 mg/kg/day (\geq 56 μ M • h) in the 4-week toxicity study, and these changes were not completely reversed by the end of the 4-week recovery period. There was no consistent correlation with any clinical biomarkers. However, in the 9-month toxicity study in dogs, no GDC-0853-related vascular inflammation was observed up to the highest dose of 10 mg/kg/day (36 μ M •h), which is considered to be the NOAEL (AUC) for the canine vascular inflammation findings.

The translatability of

these findings to humans is unknown; however, Beagle dogs are susceptible to spontaneous development of polyarteritis syndrome (Snyder et al. 1995) and may be more sensitive to any drug-induced effects. Further, there are several examples of approved therapies for which there is no correlation between the finding of vasculitis in dogs or rats at clinically relevant exposures and adverse outcomes in patients (FDA 2011).

As a safety risk-mitigation measure, patients with a history of vasculitis, including RA-associated vasculitis, will be excluded from the study, and CBC, creatinine, and urinalysis will be monitored in all patients during the study. Study drug should be discontinued in any patient who develops an adverse event of vasculitis, and the patient should enter safety follow-up.

Guidelines for management of GDC-0853 in the event of vasculitis in patients are provided in Table 3. Please refer to the GDC-0853 Investigator's Brochure for further details.

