5.1.1.9 Malignancy

The impact of BTK inhibition on the development of malignancies is not known; however, malignancies have been identified as a potential concern for immunomodulatory agents. Malignancies have been reported in patients with XLA, including lymphoreticular malignancies, gastric and colorectal adenocarcinoma, and squamous cell carcinoma of the lung.

Patients with a history of cancer, including hematologic malignancy and solid tumors, within 10 years before screening will be excluded from the blinded Study GA29350. Basal or squamous cell carcinoma of the skin that has been excised and is considered cured and in situ carcinoma of the cervix treated with apparent success by curative therapy more than 1 year prior to screening in the blinded study are not exclusionary.

All malignancies are considered adverse events of special interest and should be reported to the Sponsor in an expedited manner as outlined in Section 5.2.3.

Guidelines for management of GDC-0853 in the event of malignancies in patients are provided in Table 3. Please refer to the GDC-0853 Investigator's Brochure for further details.

5.1.2 Management of GDC-0853 in Patients Who Experience Specific Adverse Events

Guidelines for management of GDC-0853 in patients who experience specific adverse events are provided in Table 3. For a potential dose reduction for other adverse events not listed in the table, please consult the Medical Monitor.

 Table 3
 Guidelines for Management of GDC-0853 in Patients Who Experience Specific Adverse Events

Event	Action to Be Taken ^a
Infection ^b	
Serious infection or any infection requiring treatment with an IV antimicrobial agent	Discontinue GDC-0853 and report event as adverse event of special interest.
Self-limited non-serious infections that require treatment	Withhold GDC-0853 during antimicrobial therapy. GDC-0853 may be resumed after consultation with the Medical Monitor.
Bleeding	Any Grade ≥2 bleeding event is considered an adverse event of special interest and should be reported to the Sponsor in an expedited manner.
	For serious (Grade 3 or above) bleeding events, withhold GDC-0853 and consult with the Medical Monitor.
Neutropenia ^c	
Grade 2: ANC >1000-1500/mm ³	Maintain GDC-0853 dosing.

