Grade 3: ANC 500–1000/mm ³	For the first occurrence of a Grade 3 neutrophil count decreased, withhold GDC-0853 and recheck the CBC in 7 days. If the neutrophil count has recovered to Grade 1 (>1500/mm³) or normal range, resume dosing at 200 mg BID. If the Grade 3 neutropenia persists, discontinue GDC-0853. Second occurrence of Grade 3 neutrophil count decreased: Withhold GDC-0853, recheck CBC in 7 days. If the
	neutrophil count has recovered to Grade 1 (>1500/mm³) or normal range, restart GDC-0853 at the lower dose of 200 mg QD. If the Grade 3 neutrophil count decreased persists, discontinue GDC-0853.
	Third occurrence of Grade 3 neutrophil count decreased: Discontinue GDC-0853.
Grade 4: ANC < 500/mm ³	For Grade 4 neutrophil count decreased: discontinue GDC-0853.
Thrombocytopenia ^d	
Grade 1: PLT > 75,000/mm ³	In the absence of bleeding event(s), maintain GDC-0853 dosing.
Grade 2: PLT 50,000-75,000/mm	First occurrence of Grade 2 platelet count decreased: withhold GDC-0853, recheck CBC in 7 days. If platelet count has recovered to Grade 1 or has returned to the normal range, and in the absence of bleeding resume dosing at 200 mg BID.
	Second occurrence of Grade 2 platelet count decreased: withhold GDC-0853, recheck CBC in 7 days. If platelet count has recovered to Grade 1 or has returned to the normal range and in the absence of bleeding restart GDC-0853 at the lower dose of 200mg QD.
	Third occurrence of Grade 2 platelet count decreased: Discontinue GDC-0853.

Table 3 Guidelines for Management of GDC-0853 in Patients Who Experience Specific Adverse Events (cont.)

Event	Action to Be Taken ^a
Grade ≥ 3: PLT < 50,000/mm ³	For Grade 3 or greater platelet count decreased: discontinue GDC-0853.
Gastrointestinal effects	
Nausea, vomiting, and/or diarrhea	Manage according to site institutional guidelines. Consider administration of GDC-0853 with food as possible mitigation strategy.
	Consider reducing GDC-0853 dose to 200 mg QD and discuss with Medical Monitor.
Malignancy	
Any malignancy (with the exception of non-serious local and resectable basal or squamous cell carcinoma of the skin).	Discontinue GDC-0853. Report event as an adverse event of special interest to the Sponsor in an expedited manner.
Hepatotoxicity	
Any AST or ALT $> 3.0-5.0 \times ULN$	Withhold GDC-0853 and consult with the Medical Monitor.
AST or ALT elevation >3×ULN in	Discontinue GDC-0853.

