combination with total bilirubin >2 × ULN, of which at least 35% is direct bilirubin, or clinical jaundice	Report event as adverse event of special interest to the Sponsor in an expedited manner.
Any AST or ALT $> 5 \times ULN$	Discontinue GDC-0853.
	Elevations of AST or ALT of $> 5 \times ULN$ should be reported as adverse event(s) of special interest to the Sponsor in an expedited manner.
Cardiovascular effects	
Sustained (at least two ECG measurements > 30 minutes apart) QTcF that is > 500 msec and/or > 60 msec longer than the baseline value	Unless there is a clear alternative cause other than study drug, discontinue GDC-0853 ^e

Table 3 Guidelines for Management of GDC-0853 in Patients Who Experience Specific Adverse Events (cont.)

Event	Action to Be Taken ^a
Sustained absolute QTcF that is > 515 msec	Unless there is a clear alternative cause other than study drug, discontinue GDC-0853 ^e
An episode of torsades de pointes or a new ECG finding of clinical concern	Unless there is a clear alternative cause other than study drug, discontinue GDC-0853 ^e
Vascular Inflammation	
Vasculitis	Consult with the Medical Monitor
Hypersensitivity reactions	
Fever, chills, pruritis, urticaria, angioedema, and skin rash	Treat patient according to the standard of care for management of anaphylaxis/anaphylactoid or a hypersensitivity reaction.
Cardiopulmonary reactions, including chest pain, dyspnea, hypotension, or hypertension	Discontinue GDC-0853.
Persistent gastrointestinal symptoms (e.g., crampy abdominal pain, vomiting)	

CBC = complete blood count; IV = intravenous; MTX = methotrexate; PLT = platelet count; ULN = upper limit of normal.

- ^a Any patient who discontinues GDC-0853 should enter safety follow-up if possible.
- b Appropriate laboratory investigations, including but not limited to cultures, should be performed to establish the etiology of any serious infection.
- ^c Patients withdrawn from the study because of a reduced neutrophil count must be followed closely for signs of infection, with treatment as deemed appropriate by the investigator, including discontinuation of MTX if indicated, and must have a repeat WBC count with differential performed weekly until the ANC is above 1000 cells/mm³ (1.0 × 10⁹/L) within 2 months (or sooner if deemed necessary by the investigator), a hematology referral is recommended.

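### Table 3 omits the vasculitis stopping rule: Sections 1.3 and 5.1.1.8 say discontinue GDC-0853, but the table row asks only for a consultation

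*Combined protocol and SAP*

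**What the plan says.** Four places in the current Version 2 text bear on a patient who develops vasculitis.

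- **Section 1.3 (benefit-risk, Vasculitis):** "Study drug should be discontinued in any patient who develops an adverse event of vasculitis, and the patient should enter the safety follow-up period".
- **Section 5.1.1.8:** "Study drug should be discontinued in any patient who develops an adverse event of vasculitis, and the patient should enter safety follow-up". As in Section 1.3, there is no grade threshold and no exception.
- **Section 5.1.1.8, next paragraph:** "Guidelines for management of GDC-0853 in the event of vasculitis in patients are provided in Table 3".
- **Section 5.1.2, Table 3, Vasculitis row:** "Consult with the Medical Monitor". That is the complete entry.

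For dose changes and stopping in general, Section 4.2.2.1 says: "Guidelines for dose reduction and treatment interruption or discontinuation are provided in Section 5.1". Section 5.1 contains both the text of 5.1.1.8 and Table 3. Nothing says which governs if they differ.

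**The concern.** Table 3 is the page a site is likely to open when an event occurs, and Section 5.1.1.8 sends it there. For vasculitis the table drops the one action that the benefit-risk section relies on as mitigation. A patient managed from the table may keep taking the drug until the Medical Monitor is reached, or beyond if the Medical Monitor agrees, and two sites could handle the same event differently.

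The issue is patient safety. No endpoint or analysis depends on it. According to Section 5.1.1.8, the dog lesions had not fully reversed after a 4-week recovery period and showed no consistent clinical biomarker, so laboratory monitoring cannot be relied on to show that continued dosing is safe. Vasculitis is not an adverse event of special interest under Section 5.2.3, so a non-serious case carries no 24-hour report to the Sponsor. After Week 12, the scheduled safety visits are at Weeks 24, 36 and 52 (Appendix 1), at intervals of 12, 12 and 16 weeks.

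**Working it through.** The plan states no figure to reproduce. The check compares texts, with simple arithmetic for scale.

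**1. The instructions side by side**

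| Place | Stop drug? | Enter safety follow-up? | Consult? |
|---|---|---|---|
| Section 1.3 | Yes | Yes | Not mentioned |
| Section 5.1.1.8 | Yes | Yes | Not mentioned |
| Table 3, Vasculitis | Not mentioned | Not mentioned | Yes |
| Section 4.5.2 list | Vasculitis not listed | n/a | n/a |

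Footnote a to Table 3 sends patients who discontinue into safety follow-up. It applies once the drug has been stopped and does not itself require stopping.

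**2. Does consultation in Table 3 imply a pause in dosing?** Two other rows show how the table words that. Bleeding: "For serious (Grade 3 or above) bleeding events, withhold GDC-0853 and consult with the Medical Monitor". AST or ALT above 3 and up to 5 × ULN: "Withhold GDC-0853 and consult with the Medical Monitor". Where a pause is wanted pending consultation, the table states it. Read against these rows, consultation alone suggests that dosing need not stop.

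**3. Is the row unusual?** Event rows: infection 2, bleeding 1, neutropenia 3, thrombocytopenia 3, gastrointestinal 1, malignancy 1, hepatotoxicity 3, cardiovascular 3, vasculitis 1, hypersensitivity 1.

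2 + 1 + 3 + 3 + 1 + 1 + 3 + 3 + 1 + 1 = 19

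Counting hypersensitivity as one row, 18 give some dosing action (maintain, withhold, reduce or discontinue) for at least some grade. The gastrointestinal action is only to consider a reduction. Vasculitis is the one row with none. The count depends on merging the hypersensitivity entries, whose layout is unclear in the text available, so it is supporting detail only.

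**4. Planned dosing that could remain** (52 weeks minus event week):

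- Event at Week 12: 52 − 12 = 40 weeks
- Event at Week 24: 52 − 24 = 28 weeks
- Event at Week 36: 52 − 36 = 16 weeks

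These are ceilings and require the Medical Monitor to agree to continued dosing.

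**5. Exposure margin.** Section 3.3.1 expects mean AUC over 24 hours below 10 μM·h. Section 5.1.1.8 gives 36 μM·h as the no-adverse-effect level for vascular inflammation in the 9-month dog study, and 56 μM·h as the level at which it appeared in the 4-week study.

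- 36 / 10 = 3.6
- 56 / 10 = 5.6

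Because 10 is an upper bound on the expected mean, the margins are at least 3.6-fold and 5.6-fold.

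**The case against.** The strongest reply is that this is an omission and not a contradiction. Consulting neither permits continued dosing nor forbids stopping, and a site can do both. Section 5.1.1.8 is also the only risk subsection of 5.1.1 that states the GDC-0853 stopping rule in its own text, so its table row could be read as adding a consultation to a rule already given. Continued dosing would need the Medical Monitor to go along with it against two explicit sentences.

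There are other safeguards. The investigator or Sponsor may withdraw a patient whose safety is in jeopardy (Section 4.5.1). Serious events are reported within 24 hours. Treating vasculitis with intravenous or intramuscular steroids, cyclophosphamide, rituximab or mycophenolate would itself force discontinuation (Sections 4.3.2 and 4.5.2). The exposure margins are wide, and beagles are noted as prone to spontaneous arteritis.

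Part of this stands. The instructions can be followed together, the expected number of affected patients may be small, and the safeguards narrow the gap. The absence of vasculitis from the Section 4.5.2 list also carries no weight. That list, introduced by "Patients must discontinue study treatment if they experience any of the following", omits AST or ALT above 5 × ULN and sustained QTcF prolongation too, and Table 3 tells sites to discontinue for those (for QTcF, unless there is a clear alternative cause).

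The reading that the row merely adds consultation is weaker. Section 1.3 also states the stop for serious infection in its text, and Table 3 repeats that stop in full. A non-serious case treated without a prohibited drug triggers none of the automatic safeguards.

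**Conclusion.** The concern holds. Two sections set discontinuation as the response to any vasculitis event, and the table to which sites are sent does not carry it. Whether this is called a conflict or an omission, the Table 3 row is wrong as written if the stated mitigation is intended, and Sections 1.3 and 5.1.1.8 are wrong if it is not.

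The effect is confined to vasculitis events managed from Table 3 without regard to the text. How many there would be cannot be estimated, because the documents give no frequency. Exposure to the inconsistency runs from the time taken to reach the Medical Monitor up to the ceilings of 40, 28 or 16 weeks. The wide exposure margins point to low expected harm, with relevance to humans unknown by the protocol's own account. It should be corrected because it is an inconsistent stopping instruction for a risk the protocol itself names.

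**What to change.** Change the Vasculitis row of Table 3 to instruct sites to discontinue GDC-0853, enter the patient into safety follow-up and consult the Medical Monitor.

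If the safety team wants case-by-case handling, amend the sentences in Sections 1.3 and 5.1.1.8 to say so, and have the Table 3 row withhold drug until the consultation has taken place, as the bleeding and transaminase rows do.

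Adding vasculitis to the Section 4.5.2 list is optional tidying. If that list is opened, the liver and QTcF stops should be reconciled at the same time.

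The cost is a few words in the next amendment and a note to sites. Design, visits and sample size are unchanged.

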5.1.1.9 Malignancy

The impact of BTK inhibition on the development of malignancies is not known; however, malignancies have been identified as a potential concern for immunomodulatory agents. Malignancies have been reported in patients with XLA, including lymphoreticular malignancies, gastric and colorectal adenocarcinoma, and squamous cell carcinoma of the lung.

Patients with a history of cancer, including hematologic malignancy and solid tumors, within 10 years before screening will be excluded from the blinded Study GA29350. Basal or squamous cell carcinoma of the skin that has been excised and is considered cured and in situ carcinoma of the cervix treated with apparent success by curative therapy more than 1 year prior to screening in the blinded study are not exclusionary.

All malignancies are considered adverse events of special interest and should be reported to the Sponsor in an expedited manner as outlined in Section 5.2.3.

Guidelines for management of GDC-0853 in the event of malignancies in patients are provided in Table 3. Please refer to the GDC-0853 Investigator's Brochure for further details.

5.1.2 Management of GDC-0853 in Patients Who Experience Specific Adverse Events

Guidelines for management of GDC-0853 in patients who experience specific adverse events are provided in Table 3. For a potential dose reduction for other adverse events not listed in the table, please consult the Medical Monitor.

 Table 3
 Guidelines for Management of GDC-0853 in Patients Who Experience Specific Adverse Events

Event	Action to Be Taken ^a
Infection ^b	
Serious infection or any infection requiring treatment with an IV antimicrobial agent	Discontinue GDC-0853 and report event as adverse event of special interest.
Self-limited non-serious infections that require treatment	Withhold GDC-0853 during antimicrobial therapy. GDC-0853 may be resumed after consultation with the Medical Monitor.
Bleeding	Any Grade ≥2 bleeding event is considered an adverse event of special interest and should be reported to the Sponsor in an expedited manner.
	For serious (Grade 3 or above) bleeding events, withhold GDC-0853 and consult with the Medical Monitor.
Neutropenia ^c	
Grade 2: ANC >1000-1500/mm ³	Maintain GDC-0853 dosing.
Grade 3: ANC 500–1000/mm ³	For the first occurrence of a Grade 3 neutrophil count decreased, withhold GDC-0853 and recheck the CBC in 7 days. If the neutrophil count has recovered to Grade 1 (>1500/mm³) or normal range, resume dosing at 200 mg BID. If the Grade 3 neutropenia persists, discontinue GDC-0853. Second occurrence of Grade 3 neutrophil count decreased: Withhold GDC-0853, recheck CBC in 7 days. If the
	neutrophil count has recovered to Grade 1 (>1500/mm³) or normal range, restart GDC-0853 at the lower dose of 200 mg QD. If the Grade 3 neutrophil count decreased persists, discontinue GDC-0853.
	Third occurrence of Grade 3 neutrophil count decreased: Discontinue GDC-0853.
Grade 4: ANC < 500/mm ³	For Grade 4 neutrophil count decreased: discontinue GDC-0853.
Thrombocytopenia ^d	
Grade 1: PLT > 75,000/mm ³	In the absence of bleeding event(s), maintain GDC-0853 dosing.
Grade 2: PLT 50,000-75,000/mm	First occurrence of Grade 2 platelet count decreased: withhold GDC-0853, recheck CBC in 7 days. If platelet count has recovered to Grade 1 or has returned to the normal range, and in the absence of bleeding resume dosing at 200 mg BID.
	Second occurrence of Grade 2 platelet count decreased: withhold GDC-0853, recheck CBC in 7 days. If platelet count has recovered to Grade 1 or has returned to the normal range and in the absence of bleeding restart GDC-0853 at the lower dose of 200mg QD.
	Third occurrence of Grade 2 platelet count decreased: Discontinue GDC-0853.

Table 3 Guidelines for Management of GDC-0853 in Patients Who Experience Specific Adverse Events (cont.)

Event	Action to Be Taken ^a
Grade ≥ 3: PLT < 50,000/mm ³	For Grade 3 or greater platelet count decreased: discontinue GDC-0853.
Gastrointestinal effects	
Nausea, vomiting, and/or diarrhea	Manage according to site institutional guidelines. Consider administration of GDC-0853 with food as possible mitigation strategy.
	Consider reducing GDC-0853 dose to 200 mg QD and discuss with Medical Monitor.
Malignancy	
Any malignancy (with the exception of non-serious local and resectable basal or squamous cell carcinoma of the skin).	Discontinue GDC-0853. Report event as an adverse event of special interest to the Sponsor in an expedited manner.
Hepatotoxicity	
Any AST or ALT $> 3.0-5.0 \times ULN$	Withhold GDC-0853 and consult with the Medical Monitor.
AST or ALT elevation >3×ULN in	Discontinue GDC-0853.
combination with total bilirubin >2 × ULN, of which at least 35% is direct bilirubin, or clinical jaundice	Report event as adverse event of special interest to the Sponsor in an expedited manner.
Any AST or ALT $> 5 \times ULN$	Discontinue GDC-0853.
	Elevations of AST or ALT of $> 5 \times ULN$ should be reported as adverse event(s) of special interest to the Sponsor in an expedited manner.
Cardiovascular effects	
Sustained (at least two ECG measurements > 30 minutes apart) QTcF that is > 500 msec and/or > 60 msec longer than the baseline value	Unless there is a clear alternative cause other than study drug, discontinue GDC-0853 ^e

Table 3 Guidelines for Management of GDC-0853 in Patients Who Experience Specific Adverse Events (cont.)

Event	Action to Be Taken ^a
Sustained absolute QTcF that is > 515 msec	Unless there is a clear alternative cause other than study drug, discontinue GDC-0853 ^e
An episode of torsades de pointes or a new ECG finding of clinical concern	Unless there is a clear alternative cause other than study drug, discontinue GDC-0853 ^e
Vascular Inflammation	
Vasculitis	Consult with the Medical Monitor
Hypersensitivity reactions	
Fever, chills, pruritis, urticaria, angioedema, and skin rash	Treat patient according to the standard of care for management of anaphylaxis/anaphylactoid or a hypersensitivity reaction.
Cardiopulmonary reactions, including chest pain, dyspnea, hypotension, or hypertension	Discontinue GDC-0853.
Persistent gastrointestinal symptoms (e.g., crampy abdominal pain, vomiting)	

CBC = complete blood count; IV = intravenous; MTX = methotrexate; PLT = platelet count; ULN = upper limit of normal.

- ^a Any patient who discontinues GDC-0853 should enter safety follow-up if possible.
- b Appropriate laboratory investigations, including but not limited to cultures, should be performed to establish the etiology of any serious infection.
- ^c Patients withdrawn from the study because of a reduced neutrophil count must be followed closely for signs of infection, with treatment as deemed appropriate by the investigator, including discontinuation of MTX if indicated, and must have a repeat WBC count with differential performed weekly until the ANC is above 1000 cells/mm³ (1.0 × 10⁹/L) within 2 months (or sooner if deemed necessary by the investigator), a hematology referral is recommended.
- Patients withdrawn from the study because of a reduced platelet count must have a repeat platelet count weekly until the count is above 100,000 cells/mm³ (100×10⁹/L); additional management and treatment should be as deemed appropriate by the investigator, including discontinuation of MTX if indicated. If the platelets do not return to above 100,000 cells/mm³ (100×10⁹/L) within 2 months (or sooner if deemed necessary by the investigator), a hematology referral is recommended.
- In rare circumstances, it may be acceptable to resume GDC-0853, provided that any ECG abnormalities have resolved and that the patient is appropriately monitored. Clinical judgment should be applied and discussion with the Medical Monitor should occur.

